Our division has recently described the feasibility and utility of the use NIV using a RAM Nasal Cannula (NIV/RAM-NC) in the outpatient setting [1]. NIV/RAM-NC inpatient initiation has become more common as more data are available about the use of this new technology. Standardized protocols of how NIV/RAM-NC should be implemented and monitored are lacking here at both the inpatient and outpatient site in Children’s Memorial Hermann Hospital.

Rationale:

NIV/RAM-NC has the potential to improve transition from invasive ventilation to NIV. In the process of weaning and depending on the underlying pulmonary pathophysiologic disorder, patients may require positive pressure for long-term management in order to be discharged from hospital. At this time, the availability of NIV interfaces that can be used in the outpatient setting are limited to BIPAP and CPAP with nasal or full-face mask. These approaches restrict the use of positive pressure delivery devices in the pediatric setting due

to several factors, including: patient age, weight, mask fitness, tolerability of the interface, facial developmental and skin irritation and breakdowns [7-8]. We propose the implementation of a standardized protocol to initiate NIV/RAM-NC with Trilogy mechanical ventilator at the Children Memorial Hospital inpatient and outpatient site.

Objectives:

Primary Aims:

- Implement a standardized protocol to initiate NIV/RAM-NC with Trilogy mechanical ventilator at the Children Memorial Hospital inpatient and outpatient site.

Secondary Aims:

- Explore the side effects and complications associated with the use of NIV/RAM-NC in children.

Study Design and Methods

Overview: A one-year prospective study will be conducted in order to enroll subjects to start NIV/RAM-NC. Demographic data, clinical diagnosis, NIV RAM Cannula mode and parameters, associated complications, side effects and mortality information will be collected from the electronic medical record at the end of the year. Descriptive statistics will be obtained and presented in percentage and averages.

Study Population:

Children from 0 to 21 years admitted to the Children Memorial Hermann Hospital and consulted to Pediatric Pulmonary Service for initiation of NIV/RAM-NC both at the inpatient and outpatient.

Inclusion Criteria:

Children who fail to wean from chronic respiratory support (CPAP, BiPAP, HFNC) in whom long-term ventilation is considered between 10/2016 – 10/2017 will be included.

Exclusion Criteria:

Children with minimal setting (CPAP < 5cmH₂O, HFNC < 3LPM) able to be weaned to

regular nasal cannula and patients with upper airway obstruction that may be candidates for surgical procedure will be excluded.

Study Procedures:

Patient Risks: Risk related to the use of NIV/RAM-NC include:

- Ulceration and pressure necrosis due to the interface long-term use.
- Skin breakdown and ulceration of the nasal septum
- Abdominal distension due to aerophagia
- Aspiration of gastric content
- Nasal sinus congestion
- Air trapping and risk of pneumothorax (air leak)
- Need of further procedures (ex. chest tube)

Patient Benefits:

- Prevent invasive procedures like tracheostomy tube cannulation
- Avoid the use of traditional facial interfaces for positive pressure delivery and their complications
- Potential decrease the length of the total hospitalization

Study Outcomes

Our goal is to safely initiate and monitor the use of NIV/RAM-NC implementation in the inpatient and outpatient setting at Children Memorial Hospital and promote an adequate transition to home NIV ventilation with Pediatric Pulmonary follow up.

Data Analysis Plan

At the end of the study, data will be extracted from the electronic medical record (Care4) McGovern Medical School, UT Health. Statistical collaboration from UT will be used for data analysis, if needed. Data analysis will be encrypted with a password that will be known by the principal investigator and research co-workers. Percentage analysis for the epidemiology and risk factors information from the EMR will be analyzed for each variable. Graphical analysis from multiple variables for hypothesis testing will be part of the study.

Sample size and power

Based on our experience about the use of NNIV with RAM Cannula, we expect to enroll around 50 subjects to be part of the study. No power known at this time due to the limited use of NIV/RAM-NC in the pediatric population and the scant literature on this topic. Our sample will depend on the number of patients consulted to initiate NIV/RAM-NC at the inpatient and outpatient setting.

Limitations

Limited use of NIV/RAM-NC in the pediatric population may affect our enrollment and observations. We expect to implement a protocol and describe our experience with our NIV/RAM-NC children cohort.

Confidentiality

Every effort will be made to protect the privacy of the subjects. Unique identifiers will not be stored in the final database that will be used for analytic purposes. Information such as age, sex, and ethnicity will be collected to examine the patterns of interaction, if any, among demographic subgroups. Collected data will be encrypted on a password protected USB. We will minimize the need to collect information about research subjects. Data will be collected using a linking log (saved in a different password protected USB) to avoid the use of identifiers and destroyed after 2 years. The need to access to research data should be based on a "need to know" and "minimum necessary" standard.

Upon completion of the study, electronic data will be retained by the principal investigator ([name] [name]) at the University of Texas Medical School office ([REDACTED]). All data forms will be kept in a locked file cabinet and electronic files will be password protected. Subjects will not be directly identifiable. The PI, co-investigators, and designated study staff will use the information for data analysis and manuscript preparation.

NIV/RAM-NC Implementation Inpatient Protocol:

Where will this initiative be implemented?

This quality improvement project will be implemented in Children Memorial Hermann Hospital inpatient site (Pediatric Intensive care unit [PICU] and Intermediate care unit

[IMU]) in the TMC plus at the Pediatric Pulmonary Clinics and High Risk Clinics at UTMB outpatient sites.

How will we implement this project?

INPATIENT:

- Pediatric Pulmonary Team will be consulted on patients that fail to wean from chronic respiratory support (CPAP, BiPAP, High flow Nasal Cannula in whom long-term ventilation is considered).
- Pediatric Pulmonary Team, as a consultant, will consider patient history, physical examination, previous imaging and laboratories and previous attempts to wean from respiratory support and causes of failure to wean.
- The Pulmonary team will determine which patients would potentially benefit from use of NIV/RAM-NC for long-term respiratory support and will recommend initiation of NIV/RAM-NC.
- Baseline pulmonary pathophysiology to consider NIV/RAM-NC Initiation include inability to wean from conventional ventilator support and one or combination of the following:
 - Chest Wall weakness
 - Central control abnormalities
 - Obstructive lung disease
 - Restrictive lung disease
- Indications for NIV/RAM-NC initiation can include:
 - Inability to tolerate weaning from HFNC or hospital CPAP/BPAP without sedation
 - Inability to tolerate conventional CPAP/BPAP mask interface
 - Dyspnea secondary to chest wall weakness
 - Parental desire to avoid tracheostomy tube placement
 - Obstructive sleep apnea
- Baseline workup requested before NIV/RAM-NC initiation (these would be standard elements of patient evaluation regardless of evaluation for NIV/RAM-NC)

- Blood Gas (Assess baseline hypercapnea)
- Pulse oximetry monitoring (Assess baseline hypoxemia)
- Chest X-ray (CXR), (Evaluate baseline pulmonary disease)
- ENT evaluation to evaluate for upper airway anomalies that can be fixed surgically (if apply)

OUTPATIENT:

- Pediatric Pulmonary Team will be consulted as an outpatient on patients in whom long-term ventilation is considered.
- Pediatric Pulmonary Team, as a outpatient consultant, will evaluate patient history, physical examination, previous imaging and laboratories.
- The Pulmonary team will determine which patients would potentially benefit from use of NIV/RAM-NC for long-term respiratory support and will recommend initiation of NIV/RAM-NC in the outpatient setting.
- Baseline pulmonary pathophysiology to consider NIV/RAM-NC initiation could include one of the following or combination:
 - Chest Wall weakness
 - Central control abnormalities
 - Obstructive lung disease
 - Restrictive lung disease
- Indications for NIV/RAM-NC initiation can include:
 - Inability to tolerate conventional CPAP/BPAP mask interface
 - Dyspnea secondary to chest wall weakness
 - Parental desire to avoid tracheostomy tube placement
 - Obstructive sleep apnea
- Baseline workup requested before NIV/RAM-NC initiation (these would be standard elements of patient evaluation regardless of evaluation for NIV/RAM-NC)
 - Blood Gas (Assess baseline hypercapnea)
 - Pulse oximetry monitoring (Assess baseline hypoxemia)
 - Chest X-ray (CXR), (Evaluate baseline pulmonary disease)

- ENT evaluation to evaluate for upper airway anomalies that can be fixed surgically (if apply)

What will we measure?

- Monitoring success of NIV/RAM-NC implementation will include
 - Work of breathing improvement (clinically)
 - Tachypnea improvement (Monitoring respiratory rate)
 - Hypercapnea (Monitor Blood gases)
 - Hypoxemia (Monitor pulse oximetry)
 - CXR (Evaluation of air trapping / hyperexpansion)

Interpretation and Potential Importance of Findings

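### With staggered entry and one calendar cut-off, the complication and mortality percentages describe events seen by extraction, not the risk over a defined period

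*Combined protocol and SAP*

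**What the plan says.** The document is a combined protocol and analysis plan. Under Study Design and Methods, the Overview describes the design as "A one-year prospective study will be conducted in order to enroll subjects to start NIV/RAM-NC". The Inclusion Criteria take children "in whom long-term ventilation is considered between 10/2016 – 10/2017 will be included", so entry is spread over about 12 months.

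On outcomes, the Overview says "associated complications, side effects and mortality information will be collected from the electronic medical record at the end of the year", followed by "Descriptive statistics will be obtained and presented in percentage and averages". The Data Analysis Plan also describes one extraction from the electronic record, at the end of the study, and gives no date. It adds "Percentage analysis for the epidemiology and risk factors information from the EMR will be analyzed for each variable". That sentence names epidemiology and risk factors, so the case for percentages of complications rests on the Overview.

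The only secondary aim is "Explore the side effects and complications associated with the use of NIV/RAM-NC in children". The Limitations section describes the purpose as "We expect to implement a protocol and describe our experience with our NIV/RAM-NC children cohort".

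No section gives a follow-up length per child, a fixed assessment time, a minimum follow-up, or a patient-time or time-to-event summary. Study Outcomes mentions pulmonary follow-up without a duration, and the measures listed under the heading on what will be measured have no time points.

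**The concern.** A percentage of children with a complication has a clear meaning when every child is observed for the same stated time. Here a child who starts in the first month may be observed for almost a year and one who starts in the last month for a few days, yet each counts once in the denominator. The result averages over follow-up times that the plan neither fixes nor undertakes to report.

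The consequence is one of interpretation. A reader could not tell whether the figure reflects early or longer-term risk, and could not set it beside a cohort with a different mix of follow-up. This matters most for harms that build up with use. Under Study Procedures, the list of patient risks ties ulceration and pressure necrosis to long-term use of the interface, and the section on interpretation of findings expects to describe how safe initiation is.

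**Working it through.** The plan states no event rate, so it has no figure to reproduce. The expected enrolment of around 50 (Sample size and power) comes from experience and not from a formula.

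**Inputs from the document:** entry over 12 months; about 50 children; one extraction at the end of the year or of the study; percentages as the summary.

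**Assumptions:** even accrual; cut at month 12; no loss to follow-up; true 12-month risk R = 20%; 90 days taken as 3 months.

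**Step 1, follow-up.** Time from start to cut is uniform on 0 to 12 months, with mean and median 6. Expected children with under 1, 3 and 6 months are 50 × 1/12 = 4.2, 50 × 3/12 = 12.5 and 50 × 6/12 = 25.

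**Step 2, constant hazard.** With L = −ln(1 − 0.20) = 0.2231, the expected percentage is 1 − (1 − e^(−L))/L = 1 − 0.20/0.2231 = 10.4%, or 5.19 of 50 children. A 12-month window for every child would give 20%, or 10 of 50. The 90-day risk under the same hazard is 1 − e^(−L×3/12) = 5.4%.

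**Step 3, other hazard shapes.** Let F(t) = 1 − exp(−L(t/12)^k). The expected percentage is the mean of F(t) over t from 0 to 12.

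| Shape k | Expected percentage | Share of 12-month risk | 90-day risk | Ratio to 90-day risk |
|---|---|---|---|---|
| 0.25 (early, falling) | 16.3% | 0.81 | 14.6% | 1.1 |
| 0.5 | 13.7% | 0.69 | 10.6% | 1.3 |
| 1 (constant) | 10.4% | 0.52 | 5.4% | 1.9 |
| 1.5 | 8.3% | 0.42 | 2.8% | 3.0 |
| 2 (rising) | 7.0% | 0.35 | 1.4% | 5.0 |

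**Step 4, early events only.** If all events fall evenly within month 1 and none later, the figure is 20% × (0.5 + 11)/12 = 19.2%, which is 96% of either risk.

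**Step 5, accrual pattern.** With a constant hazard and the same 20% risk, the figure is 17.7% if all children enter in the first 3 months and 2.7% if all enter in the last 3.

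**Step 6, a later cut.** If extraction is 3 months after the last entry, follow-up runs from 3 to 15 months and the constant-hazard figure is 15.2%. The spread between first and last child is still 12 months. A later calendar cut alone does not create a common window.

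**The case against.** The best case against the point has four parts.

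- **The study is descriptive.** The implementation text calls it a quality improvement project, the primary aim is to implement a protocol, and the secondary aim is to explore. A crude percentage is a valid description of what was seen by extraction. This stands, and it keeps the point small.
- **The benchmarks are not the plan's.** No section claims a 12-month or 90-day risk, or plans a comparison with another cohort. The 20% risk, even accrual and hazard shapes are all assumed. This stands, so the figures only illustrate how far one percentage can sit from different risks.
- **Initiation may mean the early period.** If most harms come soon after the start, the distortion is slight, as step 4 shows. Only one of the seven listed risks is expressly tied to long-term use. This also stands, but the documents do not say when events are expected.
- **The numbers are small.** With 5 events in 50, the exact 95% interval is 3.3% to 21.8%, which contains both the 5.4% and the 20% of step 2. Imprecision limits the practical effect, but it does not tell the reader which period the estimate refers to.

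A reader might infer that the plan will understate complications by about half. The documents do not support that. The half follows from a constant hazard and a 12-month target, neither of which the plan states. Under the same assumptions the percentage is too high if read as a 90-day risk.

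**Conclusion.** The point holds as a cheap improvement. With any single calendar cut, follow-up differs by up to 12 months and the percentage has no defined period. That conclusion does not depend on the exact date of extraction. It does assume a single cut. This is the natural reading of the Overview and the Data Analysis Plan, but the plan does not say so outright and does not date the end of the year or of the study.

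The size cannot be fixed from the documents. Under the stated assumptions it runs from slight (19.2% against a 20% risk, for events in month 1) to large (7.0% against 20%, for a rising hazard). It is likely to matter little for early events and more for harms that depend on duration of use.

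A reader might go further and conclude that the safety aim fails or that the study is invalid. The documents do not support that: no test or sample size depends on these percentages, and the stated aim is exploratory description.

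**What to change.** 1. **Fixed window.** Report complications and mortality as percentages over a set period from each child's start, for example 90 days. Count only events inside it, and extract the record after the last enrolled child has completed it. With even accrual, the expected number of children with an incomplete 90-day window falls from 12.5 of 50 at month 12 to 0 at month 15.

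2. **Rate for later harms.** Report first events per patient-month of device use, stopping the clock at first event, device stop, death or last contact, with the median and range of follow-up. For mortality, count time to death or last contact. Stopping the clock at the first event matters. In the constant-hazard example, 5.19 events over 278.9 patient-months at risk give 1.86 per 100, which equals the assumed hazard. Start and last-contact dates alone would give 50 × 6 = 300 patient-months and 1.73 per 100, or 93% of it.

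3. **Extraction date.** State it as a calendar date. If the lock cannot move, label the crude percentage *events seen by extraction* and give the median and range of follow-up beside it.

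**Cost.** Four dates per child from the same record: start, device stop, first event (including death) and last contact. No extra patients or visits are needed. Item 1 with a 90-day window moves the lock about 3 months, to about 1/2018. That takes outcome collection beyond the one-year period, so the protocol must say so and reconcile it with the minimum-necessary commitment under Confidentiality. The two-year destruction period in that section is not breached, even if counted from 10/2016. A 90-day window alone does not describe later harm, and a patient-month rate averages over time if the hazard is not constant. The fallback in item 3 needs no later lock.

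### Complications come only from a year-end chart extraction, with no planned check for most listed risks, so minor and home events are likely to be under-counted

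*Combined protocol and SAP*

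**What the plan says.** The Overview under Study Design and Methods sets out the design: "A one-year prospective study will be conducted in order to enroll subjects to start NIV/RAM-NC". It then fixes the source and timing of the safety data: "associated complications, side effects and mortality information will be collected from the electronic medical record at the end of the year". The Data Analysis Plan agrees: "At the end of the study, data will be extracted from the electronic medical record (Care4) McGovern Medical School, UT Health". Results are to be descriptive, as percentages and averages.

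The one secondary aim is "Explore the side effects and complications associated with the use of NIV/RAM-NC in children". Study Outcomes adds "Our goal is to safely initiate and monitor the use of NIV/RAM-NC implementation in the inpatient and outpatient setting", and the section on interpretation expects to describe how safe initiation is.

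Clinical monitoring is listed under What will we measure?, introduced by "Monitoring success of NIV/RAM-NC implementation will include". The items are work of breathing, respiratory rate, blood gases, pulse oximetry and chest X-ray, without time points. Confidentiality mentions data forms, but only to say how they are stored. The sites include "Pediatric Pulmonary Clinics and High Risk Clinics at UTMB outpatient sites". Limitations discusses the small number of users and does not mention incomplete recording of complications.

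**The concern.** Enrolment is prospective, but no prospective ascertainment of complications is described. The protocol gives no definitions of complications, no schedule for looking for them and no way to capture events at home. Several listed risks are of a kind that reaches the chart only if someone looks and writes it down. Because the analysis is a simple percentage with no category for children not assessed, a blank chart will in practice be read as no event.

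At stake is the only secondary aim. A low complication percentage at the end of the year could mean that the device was well tolerated or that minor harm was not charted, and the plan offers no means of telling these apart. In addition, data first assembled at the end of the year cannot be tabulated across children while others are still being started.

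**Working it through.** **Listed risks against planned monitoring.** The left column comes from Patient Risks, the right from What will we measure?.

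| Listed risk | Check stated in the monitoring list |
|---|---|
| Pressure injury from the interface | none |
| Skin or septal injury at the nose | none |
| Abdominal distension | none |
| Aspiration | none stated |
| Nasal or sinus congestion | none |
| Air trapping, with risk of pneumothorax | chest X-ray, for air trapping and hyperexpansion |
| Further procedures such as a chest tube | none stated; the procedure itself would normally be charted |

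A film or an oximetry reading might incidentally reveal an air leak or aspiration, but air trapping is the only listed risk that the monitoring names.

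**Size, by illustration.** There is no plan figure to reproduce: about 50 subjects (Sample size and power) is an enrolment forecast without an event rate, alpha or power. Inputs:

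- n = 50, from the protocol.
- p, the true share of children with a given complication: assumed, 2% to 20%.
- s, the share of those events that reach the chart: assumed, 50% to 100%.
- No false positives: assumed.

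The expected observed rate is p × s. The chance of seeing at least one event is 1 − (1 − p × s)^50. Coverage is the probability that the exact (Clopper-Pearson) 95% interval, calculated from the charted count, contains the true p.

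| s | p = 20%: observed rate | expected count | coverage | p = 10%: observed rate | coverage |
|---|---|---|---|---|---|
| 100% | 20% | 10 | 96.7% | 10% | 97.0% |
| 90% | 18% | 9 | 95.5% | 9% | 97.9% |
| 75% | 15% | 7.5 | 88.7% | 7.5% | 97.6% |
| 50% | 10% | 5 | 56.9% | 5% | 92.3% |

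For scale, the exact interval for 10/50 is 10.0% to 33.7%, a half-width of (33.7 − 10.0)/2, or about 12 points. The shortfalls at p = 20% are 2, 5 and 10 points.

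For rarer events, the chance of seeing at least one in 50 children is:

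| s | p = 5% | p = 2% |
|---|---|---|
| 100% | 92.3% | 63.6% |
| 90% | 90.0% | 59.7% |
| 75% | 85.2% | 53.0% |
| 50% | 71.8% | 39.5% |

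A zero count shows the same problem. With 0/50 the exact two-sided upper limit is 7.1%, but that limit applies to the charted rate. At s = 50% it corresponds to a true rate of 7.1/0.5 = 14.2%.

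**The case against.** The strongest reply is that chart entries are made at the time of care and only their extraction is late. Prospective enrolment with later abstraction is an ordinary design and no contradiction. Bedside monitoring is listed, pulmonary follow-up is intended, and data forms are mentioned. This stands. A reader might infer that nothing is recorded prospectively, or that the goal of monitoring cannot be met; the documents support neither. The gap is in planned ascertainment of complications and in aggregate review, not in care at the bedside.

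It is also fair to say that direction is not certain for every item. Death, chest tube placement and pneumothorax are unlikely to go uncharted. Distension, congestion or aspiration may come from the underlying illness and be attributed to the device, since there is no attribution rule. A claim that every complication percentage is biased downward would therefore go too far.

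Two further readings are tempting. One is that uneven charting will produce a false difference between inpatients and outpatients; no comparison of complication rates by setting is planned. The other is that the outpatient clinics use a different record system; that would be an inference from an institution label, and the documents do not say what Care4 covers. It is a question to settle, not a finding.

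Finally, the project is described as quality improvement, its primary aim is implementation, and its safety aim is exploratory. No visit schedule is given, so the cost of a form cannot be verified in detail, and Confidentiality promises to limit data collection. These points limit the weight of the concern and argue for a short form. They do not supply the missing assessments.

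**Conclusion.** The point holds as a likely under-count of minor and home events (skin or septal injury, distension, congestion). It rests on two things in the text: the only stated source is one extraction at the end, and the monitoring list names one of the listed risks. It does not extend with the same force to deaths or chest tubes.

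The size is unknown. Under the assumed capture rates the effect is small at 90% and material at 50%, where a true 20% becomes 10% and interval coverage falls to 56.9%. For a true 10% rate, coverage stays at 92.3% or above throughout, because the interval is wide at n = 50. None of these capture rates comes from the documents.

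The year-end dataset cannot support aggregate safety review during the study, although individual children are monitored. The change should be made: it is inexpensive and removes an ambiguity that no later analysis can resolve. Because the aim is secondary and exploratory, the point does not put the study as a whole in doubt.

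**What to change.** In the Overview, replace the year-end collection of complications with prospective recording:

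- At pulmonary-team contacts that already occur, inpatient and outpatient, complete a one-page form listing each item under Patient Risks as yes, no or not assessed, with onset date. The onset date also helps to separate events that preceded the device.
- Include one question to the caregiver about events since the last contact, to reach events at home.
- Use the medical record to confirm and supplement the form, and state in the Data Analysis Plan whether Care4 covers the outpatient clinics. If it does not, name the record that does.
- Report each complication as a percentage of children assessed, with an exact 95% confidence interval, and show the number not assessed.
- Add to Limitations that minor events may still be under-recorded.

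Periodic tabulation of cumulative counts, for example quarterly, would then be possible and is optional.

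The cost is protocol wording, a short form and a few minutes per contact. The new data are limited to risks that the protocol already lists. Reported rates will probably be higher than under chart extraction alone, and the text should say so in advance. Only data recording changes; eligibility and treatment do not.

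### Complications, side effects and deaths are to be reported as percentages with no measure of precision, although about 50 children are to support a description of safety (minor; a reporting improvement)

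*Combined protocol and SAP*

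**What the plan says.** Safety is a secondary, exploratory aim: "Explore the side effects and complications associated with the use of NIV/RAM-NC in children". The Overview says that "associated complications, side effects and mortality information will be collected from the electronic medical record at the end of the year", and then states how results will be shown: "Descriptive statistics will be obtained and presented in percentage and averages".

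The Data Analysis Plan adds percentages for each variable taken from the record, and graphical work across several variables that is said to serve hypothesis testing. It names no test, error level or interval. It leaves statistical collaboration to be called on if needed.

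The Patient Risks list ("Risk related to the use of NIV/RAM-NC include") includes pressure necrosis, aspiration, pneumothorax and the possible need for a chest tube.

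Under Sample size and power, "we expect to enroll around 50 subjects to be part of the study"; power is said to be unknown because use is limited and literature scant, and "Our sample will depend on the number of patients consulted to initiate NIV/RAM-NC". Limitations says the authors expect to "describe our experience with our NIV/RAM-NC children cohort". The Interpretation section goes further and expects to describe the safety of initiation in the paediatric population.

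**The concern.** With about 50 children, some of the listed risks may well be seen once or not at all. Under the stated presentation, such a risk appears as 0% or 2%. Neither figure shows by itself which underlying rates are still compatible with the data, and 0% for a risk such as pneumothorax is easily read as absence of risk.

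Sampling error counts for less when a team only lists what happened to its own patients. It counts for more once those percentages support a statement about safety in paediatric patients generally, which is how the Interpretation section is worded. The plan also foresees a manuscript (Confidentiality section), so the percentages will reach outside readers.

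The sample-size section explains the missing power statement by limited use and scant literature. That does not explain the absence of precision, which depends only on the number of children and the event count.

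**Working it through.** **The plan's own figure.** The only number is the expected enrolment of about 50. It rests on the team's experience. The plan gives no error level, event rate, precision target or power, so the 50 can be neither reproduced nor refuted, and no error in it is claimed.

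**Inputs.**
- n: about 50 (Sample size and power). It is not fixed, because it follows the number of consults, so I show an assumed range of 30 to 60.
- Confidence level: 95%, assumed.
- Event counts: 0, 1 and 2, assumed. The documents give no complication rates.

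**Zero events, exact (Clopper-Pearson) two-sided 95%.** The lower limit is 0 and the upper limit is 1 − 0.025^(1/n).

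| n | Calculation | Upper limit |
|---|---|---|
| 30 | 1 − 0.025^(1/30) | 11.6% |
| 40 | 1 − 0.025^(1/40) | 8.8% |
| 50 | 1 − 0.025^(1/50) | 7.1% |
| 60 | 1 − 0.025^(1/60) | 6.0% |

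**One or two events at n = 50.** With x events, the exact limits are the 2.5% quantile of Beta(x, n − x + 1) and the 97.5% quantile of Beta(x + 1, n − x).
- 1/50 (2%): 0.1% to 10.6%.
- 2/50 (4%): 0.5% to 13.7%.

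**Does the choice of interval matter?** The Wilson two-sided upper limit for 0/50 is z²/(n + z²) with z = 1.96, which is 3.84/53.84 = 7.1%, the same as the exact value to one decimal. Sidedness does matter: the one-sided exact 95% limit for 0/50 is 1 − 0.05^(1/50) = 5.8%. Both must therefore be fixed in advance.

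**Another view of the same uncertainty.** A complication with a true rate of 2% (assumed) would go entirely unseen in 50 children with probability 0.98^50 = 36%.

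**What these intervals leave out.** Children enter from 10/2016 to 10/2017 and data are extracted at the end of the year, with no fixed follow-up window. If they start throughout the year, follow-up could run from days to about 12 months. At least one listed risk, ulceration and necrosis from prolonged wear of the interface, depends on duration. A binomial interval on n/N has no time horizon. The plan also does not say that each listed risk will be actively looked for in each child, so a record with no entry does not show that the event did not occur.

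**The case against.** The strongest reply is that this is descriptive work. The plan calls itself a quality improvement project ("This quality improvement project will be implemented in Children Memorial Hermann Hospital inpatient site"), the primary aim is to implement a protocol, and safety is only explored. For describing a cohort, observed percentages are what was asked for, and no safety threshold or decision rule exists that an interval could change. A reader given N can also work out the interval. Most of this stands, and it is why the point is minor. It does not remove the point: the Interpretation section reaches beyond the cohort, and the plan promises percentages without committing to n/N or to a line for listed risks with no case.

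A second objection is that intervals could lend false rigour, given unequal follow-up, selection of patients by the Pulmonary team and reliance on the medical record. This stands in full and shapes the fix.

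A reader might infer that 50 children are too few. The documents do not support that, because they set no precision target. A zero-event upper limit below 5%, for example, would need 72 children two-sided (1 − 0.025^(1/72) = 4.99%; 71 children give 5.06%) or 59 one-sided (0.95^59 = 0.048), but the 5% is only illustrative.

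A reader might also infer that point percentages are all that will be presented. The Overview does not say so, and the Data Analysis Plan adds graphical work; but neither names an interval.

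**Conclusion.** The point holds as a minor, inexpensive reporting improvement. The stated presentation carries no measure of precision, while the Interpretation section expects a description of safety in paediatric patients. With no case seen in 50 children, a rate of up to 7.1% would not be excluded (11.6% with 30 children, 6.0% with 60). These figures assume zero events, a 95% level and the exact two-sided method; none of the three comes from the documents. They cover sampling error only.

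It would go too far to say that the plan contains a wrong figure, or that its safety aim is invalid. The aim is worded as exploratory and Limitations already speaks of describing one cohort. What remains is to carry that restraint into the presentation and the safety statement.

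**What to change.** 1. In the Overview, add: *Each complication, each side effect and death will be reported as n/N with percentage and exact (Clopper-Pearson) two-sided 95% confidence interval. Risks listed under Patient Risks with no case in the medical record will be included and worded as none recorded. The distribution of follow-up time, from start of NIV/RAM-NC to data extraction, will be reported alongside. The intervals reflect sampling error only; they do not account for selection of patients by the Pulmonary team, unequal follow-up, or events not recorded in the medical record.*

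2. In Sample size and power, keep the statement that enrolment depends on consults and add: *If no case of a complication is recorded, the exact two-sided 95% upper limit is 11.6% with 30 children, 8.8% with 40, 7.1% with 50 and 6.0% with 60.*

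3. In the Interpretation section, limit the safety statement to the complications, side effects and deaths recorded in this cohort, with their intervals, in line with Limitations. The description of epidemiology can stay as it is.

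The cost is a few sentences and a little more analysis. Follow-up time needs a start date for each child, which the Overview does not list among its data items and which would have to be taken from the record if it is not already extracted. No more patients are needed. The safety statement becomes slightly less favourable.
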